8.3 TIME PERIOD AND FREQUENCY FOR EVENT ASSESSMENT AND FOLLOW-UP

The occurrence of an AE or SAE may come to the attention of study personnel during study visits and interviews of a study participant presenting for medical care, or upon review by a study monitor.

All AEs including local and systemic reactions not meeting the criteria for SAEs will be captured on the appropriate CRF. Information to be collected includes event description, time of onset, clinician's assessment of severity, relationship to study product (assessed only by those with the training and authority to make a diagnosis), and time of resolution/stabilization of the event. All AEs occurring while on study must be documented appropriately regardless of relationship. All AEs will be followed to adequate resolution.

Any medical condition that is present at the time that the participant is screened will be considered as baseline and not reported as an AE. However, if the study participant's condition deteriorates at any time during the study, it will be recorded as an AE. UPs will be recorded in the data collection system throughout the study.

Changes in the severity of an AE will be documented to allow an assessment of the duration of the event at each level of severity to be performed. AEs characterized as intermittent require documentation of onset and duration of each episode.

The PI will record all reportable events with start dates occurring any time after informed consent is obtained until 7 (for non-serious AEs) or 30 days (for SAEs) after the last day of study participation. At each study visit, the investigator will inquire about the occurrence of AE/SAEs since the last visit. Events will be followed for outcome information until resolution or stabilization.

8.4 REPORTING PROCEDURES

The study clinician will complete a SAE Form within the following timelines:

- All deaths and immediately life-threatening events, whether related or unrelated, will be recorded on the SAE Form and submitted to the DCC/study sponsor

within 24 hours of site awareness. See **Section 1, Key Roles** for contact information.

- Other SAEs regardless of relationship, will be submitted to the study sponsor within 72 hours of site awareness.

All SAEs will be followed until satisfactory resolution or until the site investigator deems the event to be chronic or the adherence to be stable. Other supporting documentation of the event may be requested by the study sponsor and should be provided as soon as possible. The study sponsor will be responsible for notifying FDA of any unexpected fatal or life-threatening suspected adverse reaction as soon as possible but in no case later than 7 calendar days after the sponsor's initial receipt of the information.

8.5 STUDY HALTING RULES

The occurrence of an AE or SAE may come to the attention of study personnel during study visits and interviews of a study participant presenting for medical care, or upon review by a study monitor.

All AEs including local and systemic reactions not meeting the criteria for SAEs will be captured on the appropriate CRF. Information to be collected includes event description, time of onset, clinician's assessment of severity, relationship to study product (assessed only by those with the training and authority to make a diagnosis), and time of resolution/stabilization of the event. All AEs occurring while on study must be documented appropriately regardless of relationship. All AEs will be followed to adequate resolution.

Any medical condition that is present at the time that the participant is screened will be considered as baseline and not reported as an AE. However, if the study participant's condition deteriorates at any time during the study, it will be recorded as an AE. UPs will be recorded in the data collection system throughout the study.

Changes in the severity of an AE will be documented to allow an assessment of the duration of the event at each level of severity to be performed. AEs characterized as intermittent require documentation of onset and duration of each episode.

The PI will record all reportable events with start dates occurring any time after informed consent is obtained until 7 (for non-serious AEs) or 30 days (for SAEs) after the last day of study participation. At each study visit, the investigator will inquire about the occurrence of AE/SAEs since the last visit. Events will be followed for outcome information until resolution or stabilization.

The study does not contain specific halting rules; however, the PI and monitor may halt the study due to AE/SAE analysis.

8.6 SAFETY OVERSIGHT

Safety oversight will be under the direction of a clinical monitor with the appropriate expertise, including. The monitor and the sponsor will assess efficacy and safety data.

9 CLINICAL MONITORING

Clinical site monitoring shall be conducted to ensure that the rights and well-being of human participants are protected, that the reported trial data are accurate, complete, and verifiable, and that the conduct of the trial is in compliance with the currently approved protocol/amendment(s), with GCP, and with applicable regulatory requirement(s). Monitoring for this study will be performed by a sponsor representative. Details of clinical site monitoring are documented in a CMP. The CMP describes in detail who will conduct the monitoring, at what frequency monitoring will be done, at what level of detail monitoring will be performed, and the distribution of monitoring

reports. Monitoring Plans may vary slightly for each study site due to each study agreement. Independent audits will be conducted to ensure clinical practices are performed consistently across all participating sites.

10 STATISTICAL CONSIDERATIONS

10.1 Populations

Intent to Treat Population (ITT): Any subject enrolled who gets a pre-weighed pad for the control phase. This is expected to be 60-70 subjects.

Modified Intent to Treat Population (mITT): Any subject enrolled who gets through the control phase, is given the device and pads for the treatment period, and who uses the device such that there is at least one data point to analyze - i.e., use of the pad for at least one hour during the last 7 days of the treatment period. A subject who is not in the study at the beginning of the last 7 days of the treatment period is in the ITT population but not the mITT population. **THE mITT IS THE POPULATION THE ANALYSIS WILL BE DONE ON.**

Per Protocol Population (PP): Any subject getting through the entire treatment period and has complete data (i.e., pad weight reduction data for the last 7 days of the treatment period). For example, someone having only data for 6 out of the last 7 days of the treatment period is in the mITT population but not the PP population.

Safety Population (SP): Same as ITT.

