4.3 STUDY ENDPOINTS

The primary endpoint is the percentage reduction in mean pad weight gain per hour of >50% during the 14-day treatment phase versus the 7-day baseline phase. The PWG percentage reduction will be calculated by comparing the mean PWG over the 7-day baseline non-treatment phase with the last 7 days of the 14-day treatment phase for each individual participant.

Important secondary endpoints will be measured based on anecdotal evidence or feedback from the subjects. These secondary endpoints are as follows:

- (1) Reduction in mean number of SUI episodes per day from episodes from the 7-day baseline period to the last 7 days of the 14-day device treatment period as measured as reduction (improvement) in stress urinary incontinence episodes. Participants will record SUI episodes in the Study Diary during the baseline (7 days) and treatment (14 days). Negative values are indicative of efficacious outcome.
- (2) Change in Quality of Life as Measured by the ICIQ-LUTSqol Quality of Life Questionnaire.

The Quality of Life Questionnaire to be performed at baseline, before and after treatment phase of the study is based on 20 questions referring to areas which may have been influenced or changed by accidental urine loss and/or prolapse. These questions are assigned a value of, 1 = 'Not at all,' 2= 'Slightly,' 3 = 'Moderately,' or 4 'A lot.' Each area of changed is then assessed on a scale of 1-10 to see how much it bothers them. The Questionnaire is scored by taking the average score of items and then multiplying the average by 25 to put scores on a scale from 0 to 100. A lower score is considered less impact to quality of life and a higher score reflects more impact to quality of life. In the same manner, a reduction in scores from baseline reflects improved quality of life. A reduction on score of ≥ 3.7 is considered the Minimum Clinically Important Difference.

- (3) Evaluation of Adverse Event assessments to determine device is safe for use.

Important Exploratory Endpoints are as follows:

- (1) Participants can successfully use the device in accordance with the given Instructions for Use.
- (2) Participants will find the device comfortable enough to demonstrate compliance with the study procedures during the device treatment phase.

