5.4 PARTICIPANT WITHDRAWAL OR TERMINATION

Participants are free to withdraw from participation in the study at any time upon request. An investigator may terminate participation in the study if:

- Any clinical adverse event (AE), laboratory abnormality, or other medical condition or situation occurs such that continued participation in the study would not be in the best interest of the participant
- The participant meets an exclusion criterion (either newly developed or not previously recognized) that precludes further study participation.]

Data for patients lost to follow up/withdrawal will be collected if possible. Subjects in the ITT population but not in the mITT group will be represented in all tables except those for the primary and secondary endpoint analysis. Data from those withdrawing from or lost to follow-up in the mITT population will be used for the primary endpoint and, if there is at least one full day's worth of data on the number of SUI episodes available, then this subject will also be included in the analysis of change in number of SUI episodes. Attempts will be made to contact subjects withdrawing from or lost to follow-up to the mITT population to administer the QoL questionnaire. If successful these subjects will be included in the change in QoL analysis. For mITT subjects not completing the treatment phase, a "last observation carried forward" approach will be used (see section 10 "Statistical Considerations"). If it appears that there will not be 50 subjects in the PP population further recruitment and enrollment will be necessary.

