- Administer the Treatment Study Diary
- Physician will administer 20 devices and 28 preweighed pads to wear both device and pad simultaneously for 14 consecutive days.
- Record any adverse events

NOTE: to minimize time between pad wearing and pad weighing, participants will be mailing back all worn pads immediately upon completion of every 7-day wear to the site. The site will record the pad weights in the Pad Weigh Log form. If the participant returns for Visit #3 within 2 days of completing the 14-day wear, they may bring the remaining 7 worn pads to the visit in lieu of mailing in pads at the physician's discretion.

Visit #3 schedule shall consist of the following:

- Update Medical History, if applicable
- Perform a urinalysis and vaginal microflora swab
- Assess for any active vaginal infection
- Collect and review the Treatment Study Diary
- Collect and weigh any remaining worn pads, if applicable
- Complete the Final Questionnaire
- Complete the post-treatment Quality of Life Survey
- Record any adverse events

Procedures	Screening	Enrollment/ Baseline (Visit 1) ¹	Follow-Up (Visit 2)	Follow-Up (Visit 3)
Informed consent	X			
Demographics	X			
Medical history	X	X	X	X
Physical exam	X			X
Vital signs	X	X	X	X
Height	X			X
Weight	X			X
Human Factors and Fit Assessment	X			
Urine Pregnancy Test (if applicable)	X		X	
Urinalysis	X			X
Administer Investigational Product			X	
Adverse event evaluation		X	X	X
Vaginal swab	X		X	X
Questionnaire	X	X	X	X
Quality of Life Survey		X	X	X

(1) Enrollment must be take place within 1 week of screening. Otherwise, screening procedures must be repeated prior to enrollment

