10.3 Sample Size and Study Outcome Determination

A precision approach will be used to determine the appropriate sample size and power for the study. For power and sample size considerations a type 1 error rate (alpha) of 0.05, one-sided, will be used. Given a sample size of 50 the calculations have been done with various standard deviations to show power below and above 90% (see Table 1 below). Sixty to seventy participants will be enrolled to allow for the fifty per-protocol participants, although the analyses will be done on the mITT population.

The assumptions made for the power and sample size computations come from the Poise study (Ziv et al), where their assumption for the effect size was reduction in pad weight gain per 8 hours of 70%, with a standard deviation of 15%. The results of the study showed an 86% reduction in pad weight gain per 8 hours with a 9% standard deviation. Given those results, this study's assumptions of 60% improvement and a range of standard deviations from 15% to 20% appear conservative; thus, the expected results would indicate a successful outcome for the primary endpoint.

The computations below are based on the precision method, which in the case of this study computes a lower 95% confidence limit for the percentage change. Here we consider a changes around 60% in the explanation of the table. Different standard deviations are used with the sample size of 50.

Table 1.

n	½ width of CI	Std Dev	Power
50	5	16	0.999
50	5	17	0.991
50	5	18	0.956
50	5	19	0.869
50	5	20	0.720
50	6	20	0.995

The first entry in the table shows that if the resulting mean reduction in pad weight gain was 60% and the standard deviation of the mean percentage change was 16%, the lower limit of the 95% confidence interval for 60% would be 55%: 60% - 5% (½ width), with 99.9% probability (power). The last line in the table above shows that the resulting mean percentage change would have to be greater than 56 for the power to be 99.5% (56% - 6% ½ width = 50%, not greater than 50%) if the standard deviation was 20%. If the result was 60% the lower limit of the confidence interval would be 54%: (60% - 6%) with 99.5% power. Thus, for all lines above except 4 and 5 the endpoint was reached with greater than 90% power.

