- b. For the quality of life score there will be three measures as described in the visit schedule above. For descriptive purposes the results and change from the previous visit will be shown, as well as the change from the enrollment visit to the post-treatment visit. The changes will likely be negative scores as the QOL is expected to improve, as the instrument records lower numbers as indicating a better quality of life. For the purposes of inferential analysis, a mixed model analysis of variance on the scores will be used on the result at time t (t=baseline, post-control, post-treatment) with time as a fixed effect and subject as a random effect. Thus, the null hypothesis is that there is no significant difference from baseline/enrollment to post-treatment, i.e., that the mean change in score is 0. The alternative is that this change is less than 0. Correlation of scores within subjects will be considered as compound symmetric. The p-value indicating the significance of the least square mean score at the third time-point compared to that at the first time-point will determine if the endpoint is met.

All inferential testing will be done on the mITT population and will be one-sided. As noted above statistical significance will be reached if the relevant p-value is less than 0.0167. Results for all populations will be reported.

There is a secondary safety endpoint as described earlier in the protocol. Safety reporting using urinalysis, vaginal swab, vaginal examination, and evaluation will be descriptive and narrative in nature.

Similarly, exploratory endpoint results of comfort and successful use will be descriptive. No inferential hypotheses will be used here.

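### Women given the device who leave before the last 7 treatment days are outside the primary set, and no efficacy analysis is defined that includes them

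*Combined protocol and SAP*

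**What the plan says.** Sections 4.2 and 10.1 define the sets in the same words. The ITT is everyone enrolled who receives a pre-weighed pad for the control phase. The mITT requires completing the control phase, receiving devices and pads, and at least one hour of pad use in the last 7 treatment days. "A subject who is not in the study at the beginning of the last 7 days of the treatment period" is placed in the ITT but not the mITT.

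Three further statements bear on her:

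- Section 10.4: "All inferential testing will be done on the mITT population and will be one-sided". It then adds: "Results for all populations will be reported".
- Section 5.4: subjects in the ITT but not the mITT "will be represented in all tables except those for the primary and secondary endpoint analysis".
- Section 7.3, on treatment-phase pads: "participants will be mailing back all worn pads immediately upon completion of every 7-day wear to the site". Some first-week device data may therefore exist for a woman who leaves early, as well as her control-phase pads.

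On numbers, section 10.3 says: "Sixty to seventy participants will be enrolled to allow for the fifty per-protocol participants". Section 10.6 replaces withdrawals until 50 per-protocol women have completed.

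**The concern.** The trial has one arm and a fixed bar of 50%, so no comparator group shares the selection. If some women stop in the first week because the device is uncomfortable or does not work, the analysed set loses the women likely to have done worst, and the estimate becomes conditional on staying. The condition is slightly stricter than reaching day 8, because an hour of pad use in the last 7 days is also needed.

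The screening fit test reduces early intolerance but does not rule it out. The protocol itself treats tolerability over the treatment phase as an open exploratory question: "Participants will find the device comfortable enough to demonstrate compliance with the study procedures during the device treatment phase". Section 10.4 says the sponsor wants the endpoints for labeling and marketing of an OTC product, for which the relevant population is the women who start using it.

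Attrition would be visible in the safety tables and listings. Its effect on the >50% conclusion would not be quantified. Replacement does not create the problem; it only lowers the stoppers' share of the total.

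**Working it through.** **Can any specified analysis include these women?**

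- mITT: excluded by definition.
- Per-protocol: narrower than the mITT, so it cannot test this.
- ITT: 10.4 promises results for all populations, but 5.4 removes these women from the endpoint tables. No endpoint value or missing-data rule is given for a woman with no last-7-day pads, so an ITT efficacy result cannot be computed from the text.
- Last observation carried forward (5.4): limited to mITT subjects.

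**The plan's own figure.** Table 1 in 10.3 gives the probability that the one-sided 95% half-width is at most h with n = 50: P(χ²₄₉ ≤ 49·[h√50/(t·SD)]²), with t = 1.6766. For h = 5 and SD 16 to 20 this gives 0.9989, 0.9909, 0.9573, 0.8719 and 0.7260; for h = 6 and SD 20 it gives 0.9952. The table shows 0.999, 0.991, 0.956, 0.869, 0.720 and 0.995, so it reproduces closely and is not in dispute.

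**Inputs for the illustration.** From the documents: planned mean 60%, SD 16 and 20 (10.3); bar 50% and one-sided alpha 0.0167 (10.4). Assumed: n = 50 analysed women, and k stoppers each scored x%.

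**Formulas.**

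- N = 50 + k; mean M = (50m + kx)/N
- SS = 49s² + 50(m − M)² + k(x − M)²
- Limit = M − t(0.9833, N−1)·√(SS/(N−1))/√N

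Where a range of counts is given for stoppers scored above 0%, its lower end adds (k − 1)s² to SS, so that stoppers vary among themselves as much as stayers do.

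With k = 0 and SD 16: 60 − 2.189 × 16/√50 = 55.05. With SD 20: 53.81.

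Worked case, k = 4, x = 0, SD 16: N = 54; M = 3000/54 = 55.56; SS = 12,544 + 988 + 12,346 = 25,877 (from unrounded terms); SD = √(25,877/53) = 22.10; limit = 55.56 − 2.184 × 22.10/√54 = 48.99.

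**Limits near the crossing, mean 60% (stoppers with no spread among themselves).**

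| Score x | SD 16 | SD 20 |
|---|---|---|
| 0% | k=3: 50.33; k=4: 48.99 | k=2: 50.78; k=3: 49.42 |
| 30% | k=9: 50.23; k=10: 49.82 | k=7: 50.20; k=8: 49.77 |
| 45% | k=20: 51.79 | k=20: 51.00 |

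**Number of stoppers at which the limit first falls to 50% or below.**

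| Observed mean | Score x | SD 16 | SD 20 |
|---|---|---|---|
| 60% | 0% | 4 | 3 |
| 60% | 30% | 9–10 | 7–8 |
| 60% | 45% | more than 20 | more than 20 |
| 65% | 0% | 7 | 6 |
| 65% | 30% | 18–19 | 16–17 |
| 70% | 0% | 10 | 10 |

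With a one-sided 95% limit and mean 60%, the counts are 5 (SD 16) or 4 (SD 20) at 0%, and 11–13 at 30%. At 86% with SD 9, the result the protocol cites from the earlier device study, 20 stoppers at 0% leave the limit at 51.1; it first fails at 22.

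**Tipping score at mean 60%.** Solving limit = 50 for x: 5 stoppers must average above 15.0% (SD 16) or 21.5% (SD 20) for success to hold; 10 must average above 30.8% or 34.7%.

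**What the mITT test would conclude.** With 10 stoppers at 0% and a stayer mean of 60%, the mean over all women given the device is (50 × 60 + 10 × 0)/60 = 50%, exactly the null value. The mITT test on 50 women would still succeed with probability 0.99 (SD 16) or 0.91 (SD 20).

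**The case against.** The exclusion largely follows from the endpoint: reduction is measured over the last 7 treatment days, and a woman who left earlier has no value there. The mITT is pre-specified, stated twice, and generous to partial completers. This stands, and it is why the mITT should remain primary. It does not explain why nothing tests sensitivity to who reaches that window.

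The sentence in 10.4 on reporting all populations can be read as promising a descriptive ITT result, and 10.2 says a more detailed SAP will follow. Both are fair readings. But the first conflicts with 5.4 and gives no method for women without last-7-day pads, and the second is only a place where the missing analysis could be added.

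The size is driven by assumptions, and this stands in full. No early-stopping rate is documented. The gap of 10 to 20 women between 60–70 enrolled and 50 per-protocol is only an upper bound, because it includes control-phase losses and mITT women with incomplete days. The protocol regards 60% as conservative, and eligibility screening (tampon experience, supervised fit test) should limit early stopping.

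The remedy is imperfect. First-week pads measure a different window. A 0% score is harsh for a woman who left for reasons unrelated to the device. A woman who leaves before completing a 7-day wear may have returned no pads. These are reasons to report a tipping-point range and the reasons for stopping rather than a single imputed figure.

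**Conclusion.** The concern holds. As written, the >50% conclusion is conditional on retention into the last 7 treatment days, and no efficacy analysis covering all women given the device is defined. Whether this matters numerically depends on two unknowns: how many women stop early and how they fared.

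Under the assumption of 50 analysed women, the exclusion is decisive only if the observed mean is near the planned 60% and stoppers did poorly. Then 3–4 stoppers at 0%, or 7–10 at 30%, are enough to bring the 98.33% limit to 50% or below. It is immaterial if stoppers did nearly as well as the bar (20 at 45% still pass) or if the effect is near 86%. This is a change that should be made, not a flaw that invalidates the design.

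**What to change.** - Keep the mITT as primary and the per-protocol set as supportive.
- Pre-specify, and report beside the primary, a sensitivity analysis in all women given the device at Visit 2: last-7-day pads where present, otherwise any treatment-phase pads, otherwise 0% reduction.
- Add a tipping-point range for the assigned score, for example 0% to 45%, and a table of discontinuations by study day and reason.
- State how a woman who stops the device but stays in the study and keeps wearing pads is classified; the current definition is unclear on this.
- Remove the 5.4 exclusion from the efficacy tables so that it agrees with 10.4.
- As a separate wording point that concerns mITT women only, reconcile the "last observation carried forward" sentence in 5.4, which refers to section 10, with section 10.6, which expects no imputation.

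The cost is protocol and SAP wording, one extra analysis and one disposition table, with no new data collection. The downside for the sponsor is that the supportive estimate may be less favourable than the primary. If the observed mean is near 60% and several stoppers did poorly, its lower limit may not exceed 50%.
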